4.5.3 Infant's Assessments

4.5.3.1 Pregnancy Outcome and Infant Characteristics

At birth:

- Pregnancy and infant outcome
- Mode of delivery (vaginal delivery, instrumental delivery, scheduled or urgent cesarean section)
- Appearance, Pulse, Grimace, Activity, and Respiration (APGAR) score (1 min, 5 min, 10 min)
- Gestational age at birth
- Infant vital biometrics (weight, length, head circumference)
- Congenital malformations

Week 6 of Life (±7 days)

- Weight measurement for safety
- Feeding status: Mothers should record feeding status of the infant, i.e., whether exclusive breastfeeding, mixed feeding (partial breastfeeding along with infant formula and/or baby food), exclusive infant formula feeding, or fully weaned
- Changes to concomitant medications given to the infant should be recorded throughout the study. For administered vaccinations, see Section 4.5.4.

Months 2, 4, 6, 9, and 12:

- Growth velocity (weight, length and head circumference), using growth charts according to the WHO Child Growth Standards (WHO 2022); as well as absolute values (other standard measurements recorded by e.g., the pediatrician as part of routine postnatal care may also be used).
- Child developmental milestones in the domains of communication, gross motor, fine motor, problem solving, and personal-social, using ASQ-3.
- Feeding status: Mothers should record feeding status of the infant, i.e., whether exclusive breastfeeding, mixed feeding (partial breastfeeding along with infant formula and/or baby food), exclusive infant formula feeding, or fully weaned.

Ocrelizumab—F. Hoffmann-La Roche Ltd

• Changes to concomitant medications given to the infant should be recorded throughout the study. For administered vaccinations, see Section 4.5.4.

See Appendix 6 for time windows for infant growth velocity and child developmental milestone assessments.

One month (+30 days) after first dose of MMR vaccine (if first dose is administered at 11 months of age or later) OR 1 month (+30 days) after second dose of MMR vaccine (if first dose is administered before 11 months of age) OR at Month 13 of chronological age (+30 days) if MMR vaccine is not planned to be administered

- Weight measurement for safety
- Changes to concomitant medications given to the infant should be recorded and throughout the study. For administered vaccinations, see Section 4.5.4.

4.5.3.2 Laboratory, Biomarker, and Other Biological Samples Umbilical cord blood assessments (target collection time within one hour of birth; only for live births; no collection should occur in the event of a pregnancy interruption [i.e., therapeutic abortion or stillbirth])

• **Ocrelizumab concentration**: a serum sample will be collected for determination of ocrelizumab concentration

Week 6 of Life (±7 days)

- Lymphocyte subtypes: A blood sample will be collected to measure B-cell counts (CD19+), T-cell counts (CD3+, CD4+, CD8+), and NK cell counts (CD16+CD56+).
- **Ocrelizumab concentration:** a serum sample will be collected for determination of ocrelizumab concentration.

Note: If the infant's B-cell levels are below LLN, repeat analyses may be done at unscheduled visits at the discretion of the investigator (in consultation with the Sponsor).

Infant samples will be collected by venipuncture. As per the recommendation of the European Commission ad hoc group (2008) the total blood volume to be collected from an infant in a clinical study should not exceed 0.8–0.9 mL/kg at any time point, or 2.4 mL/kg over any 4-week period throughout the study. If the blood volume collected for an infant (as a result of these limits) is insufficient to carry out all planned assessments, Table 3 shows the order of priority for assessments.

Table 3Prioritization Order for Infant Blood Sample Assessments at
Week 6 of Life (±7 days)

Order of Priority	Assessment		
1	Any safety laboratory samples (scheduled or unscheduled and performed at the discretion of the Investigator)		
2	Lymphocyte subtypes blood sample ^a		
3	Serum ocrelizumab concentration		

NK = natural killer.

^a Blood samples will be collected to measure B-cell counts (CD19+), T-cell counts (CD3+, CD4+, and CD8+), and NK cell counts (CD16+CD56+).

One month (+30 days) after first dose of MMR vaccine (if first dose is administered at 11 months of age or later) OR 1 month (+30 days) after second dose of MMR vaccine (if first dose is administered before 11 months of age) OR at Month 13 of chronological age (+30 days) if MMR vaccine is not planned to be administered

• Lymphocyte subtypes: A blood sample will be collected to measure B-cell counts (CD19+), T-cell counts (CD3+, CD4+, CD8+) and NK cell counts (CD16+CD56+).

Note: If the infant's B-cell levels are below LLN, repeat analyses may be done at unscheduled visits at the discretion of the investigator (in consultation with the Sponsor).

• Serum antibody titers to vaccines administered as per local practice (e.g., diphtheria, tetanus, pertussis, Hib, PCV-13, HBV, and MMR)

Note: While vaccination schedules are not exactly the same from country to country, all participating countries are expected to provide the specific vaccines for the planned titer assessments

Infant samples will be collected by venipuncture. As per the recommendation of the European Commission ad hoc group (2008) the total blood volume to be collected from an infant in a clinical study should not exceed 0.8–0.9 mL/kg at any time point, or 2.4 mL/kg over any 4-week period throughout the study. If the blood volume collected for an infant (as a result of these limits) is insufficient to carry out all planned assessments, Table 4 shows the order of priority for assessments.

Table 4Prioritization Order for Infant Blood Sample Assessments1 Month (+30 days) after First/Second Dose of MMR Vaccine ORat Month 13 of Age (+30 Days)

Order of Priority	Assessment		
1	Any safety laboratory samples (scheduled or unscheduled and performed at the discretion of the Investigator)		
2	Serum titers of antibody responses to vaccines ^a		
3	Lymphocyte subtypes blood sample ^b		

Ab = antibody; IgG = immunoglobulin G; MMR = measles, mumps, and rubella; NK = natural killer; PCV-13 = 13-valent pneumococcal conjugate vaccine.

- ^a Titers of responses to vaccines administered as per local practice may include the following: anti-measles Ab IgG, anti-rubella Ab IgG, anti-mumps Ab IgG, PCV-13 Ab (all serotypes), anti-tetanus toxoid IgG, anti-diphtheria IgG, Bordetella pertussis Ab IgG, hepatitis B surface Ab, and Hemophilus influenzae B IgG.
- ^b Blood samples will be collected to measure B-cell counts (CD19+), T-cell counts (CD3+, CD4+, and CD8+), and NK cell counts (CD16+CD56+).

4.5.4 Infant Vaccination Schedule

Infants will receive vaccinations according to the immunization schedule recommended in each participating country. The safety and timing of vaccination of the infant should still be discussed with the mother, in particular the vaccination with live-attenuated vaccines (e.g., MMR) for which the results on B-cell levels at Week 6 of life may be informative. Vaccines administered from birth throughout the end of the study, should be recorded at Months 2, 4, 6, 9, and 12 as well as at 1 month (+30 days) after first or second MMR dose/Month 13 of age (+30 days) and may include *diphtheria, tetanus, pertussis*, Hib, PCV-13, HBV, and MMR.

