2. OBJECTIVES AND ENDPOINTS

This study will evaluate the potential placental transfer of ocrelizumab in women with CIS or MS (in line with the locally approved indications) whose last dose of ocrelizumab was administered anytime from 6 months before the LMP through to the first trimester of pregnancy (up to gestational Week 13), and the corresponding pharmacodynamic effects, particularly B-cell levels, in the infants.

Specific objectives and corresponding endpoints for the study are outlined below.

Table 1 Objectives and Corresponding Endpoints

Objectives	Corresponding Endpoints
Primary Outcome Measure	
• To evaluate whether infants potentially exposed to ocrelizumab during pregnancy present with postpartum B-cell depletion	 Proportion of infants with B-cell levels (CD19 + cells, absolute counts) below the LLN, measured at Week 6 of life

ASQ-3 = Ages and Stages Questionnaire, version 3; EDSS = Expanded Disability Status Scale; HBV = hepatitis B virus; Hib = Hemophilus influenzae type b; LLN = lower limit of normal; MMR = measles, mumps, and rubella; MS = multiple sclerosis; PCV-13 = 13-pneumococcal conjugate vaccine; SARS-CoV-2 = severe acute respiratory syndrome coronavirus 2; sNfl = serum neurofilament light chain; WHO = World Health Organization.

Table 1 Objectives and Corresponding Endpoints (cont.)

Objectives	Corresponding Endpoints	
Secondary Outcome Measures		
To evaluate B-cell levels in infants potentially exposed to ocrelizumab during pregnancy	 B-cell levels (CD19 + cells, absolute counts and percentage of lymphocytes) measured at Week 6 of life 	
• To evaluate whether there is placental transfer of ocrelizumab from the mother to the infant	• Serum concentration of ocrelizumab in the umbilical cord blood at birth (target time frame of blood sampling: within 1 hour after delivery)	
	 Serum concentration of ocrelizumab in the infant at Week 6 of life 	
To evaluate whether infants potentially exposed to ocrelizumab during pregnancy are able to mount humoral immune responses to clinically relevant vaccines	• Mean titers of antibody immune response(s) to common childhood vaccinations with full or partial doses given prior to 1 year, which include responses to diphtheria, tetanus, pertussis , Hib, PCV-13, MMR, and HBV	
	 Proportion of infants with positive humoral response (seroprotective titers; as defined for the individual vaccine) to vaccines 	

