Note: If the infant's B-cell levels are found to be below lower limit of normal (LLN), repeat analyses may be done at unscheduled visits at the discretion of the investigator (in consultation with the Sponsor).

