4.5.3 Infant Absolute Antibody Immune Response

The infant's antibody (Immunoglobulin [Ig]G) immune response to common childhood immunizations with full or partial doses given prior to 1 year may include (but is not limited to) responses to MMR, diphtheria, tetanus, and pertussis (DTaP), Hemophilus influenzae type b (Hib), hepatitis B virus (HBV) and 13-valent pneumococcal conjugate vaccine (PCV-13), measured 1 month after the first or second dose of MMR vaccine or at Month 13 of age (+30 days) in case MMR vaccine is not planned to be administered.

Summary statistics for each serum IgG antibody titer will be presented in the AIRI and a corresponding listing produced. Results for MMR titers will be summarized together irrespective of whether or not the infant received MMR vaccine. Analysis will be presented for the following subgroups:

- Maternal OCR exposure prior to the study in 3-month interval of before/during pregnancy (3-6 prior LMP, 0-3 month prior to LMP, 1st trimester)
- Type of feed: exclusive breast milk from birth to Month 6 vs others (including complementary feeding [breastmilk + formula milk, in various proportions] and formula feeding [no breast milk])
- Women with/without receiving postpartum ocrelizumab

A listing with all immune responses will be produce.

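### MMR titres and seroprotection are pooled over infants with and without MMR, and shown by no Week 6 B-cell status, although that result may inform live-vaccine timing

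*Protocol*

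**What the plan says.** Protocol Section 2 sets the secondary objective of finding out whether potentially exposed infants "are able to mount humoral immune responses to clinically relevant vaccines".

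Protocol 4.5.4 makes national practice the default: "Infants will receive vaccinations according to the immunization schedule recommended in each participating country". It then asks that the mother be brought into a discussion of safety and timing, "in particular the vaccination with live-attenuated vaccines (e.g., MMR) for which the results on B-cell levels at Week 6 of life may be informative". It also requires that "Vaccines administered from birth throughout the end of the study, should be recorded at Months 2, 4, 6, 9, and 12", and again at the final infant visit.

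The Week 6 count can reach the investigator before MMR is due. Protocol 3.1.3 notes: "If the infant's B-cell levels are found to be below lower limit of normal (LLN), repeat analyses may be done", at the investigator's discretion and in consultation with the sponsor.

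SAP 4.5.3 summarises each titre in the AIRI, which SAP 4.1.5 defines by availability of any titre, not by receipt of the vaccine. For MMR it states the rule explicitly: "Results for MMR titers will be summarized together irrespective of whether or not the infant received MMR vaccine". There are three subgroups. The first is timing of the mother's last dose: "Maternal OCR exposure prior to the study in 3-month interval of before/during pregnancy (3-6 prior LMP, 0-3 month prior to LMP, 1st trimester". Another is whether the mother received ocrelizumab postpartum. The remaining one is feeding: "Type of feed: exclusive breast milk from birth to Month 6 vs others".

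SAP 4.5.3.1 presents seroprotected proportions in the same set and by the same three subgroups, with no restriction to recipients.

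**The concern.** A measles, mumps or rubella titre shows ability to respond only if the vaccine was given. Putting an unvaccinated infant in the denominator makes the proportion partly a measure of vaccine uptake. In most studies that is a small blemish. Here the protocol lets the primary endpoint result inform the timing of the live vaccine, so infants with low B cells may be over-represented among those without MMR at sampling.

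Two misreadings become possible. Unvaccinated infants can make the cohort look as if some infants failed to respond. And because no titre summary is set against Week 6 B-cell status, the reader cannot see whether the few infants with low counts were vaccinated and, if so, whether they responded. Protocol 3.3 motivates the titre measurements with a study of B-cell-depleted adults whose vaccine responses were attenuated, so this is the comparison a reader will look for.

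**Working it through.** **Inputs.** 33 women and 10% dropout (Protocol 6.1, SAP 2.2). Event counts of 1 to 5 in 30 (Protocol Table 5, SAP Table 1). LLN defined as the 2.5th percentile (Protocol Appendix 7, SAP Appendix 4). Two-sided Clopper-Pearson 95% CIs for seroprotection (Protocol 6.4.2).

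**Step 1: the plan's denominator.** 33 × (1 − 0.10) = 29.7, which reproduces the stated figure of about 30. That is the number evaluable at Week 6. The number with titres may be smaller, so 30 is used for illustration.

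**Step 2: effect of pooling.** Let u be the number of infants without MMR at sampling. Assumptions, none given in the documents:
- u runs from 1 to 5, a range borrowed from the precision table;
- every recipient responds;
- no infant without MMR is seroprotected.

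Pooled proportion = (30 − u)/30. Among recipients = (30 − u)/(30 − u) = 100%, with lower limit 0.025^(1/(30 − u)).

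| u | Pooled, as planned (95% CI) | Recipients only (95% CI) |
|---|---|---|
| 1 | 29/30 = 96.7% (82.8–99.9) | 29/29 = 100% (88.1–100) |
| 2 | 28/30 = 93.3% (77.9–99.2) | 28/28 = 100% (87.7–100) |
| 3 | 27/30 = 90.0% (73.5–97.9) | 27/27 = 100% (87.2–100) |
| 4 | 26/30 = 86.7% (69.3–96.2) | 26/26 = 100% (86.8–100) |
| 5 | 25/30 = 83.3% (65.3–94.4) | 25/25 = 100% (86.3–100) |

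The recipients-only column is not a planned output.

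**Step 3: two different results, one table entry.** Take u = 3. The plan shows 27/30 = 90%. Thirty vaccinated infants with three non-responders also give 27/30 = 90%. The planned summary cannot tell these apart.

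**Step 4: sensitivity to the third assumption.** If a share s of the unvaccinated infants is seroprotected for another reason, the pooled proportion is (30 − u + s·u)/30. For u = 5 this runs from 83.3% (s = 0) to 100% (s = 1). The distortion is therefore 0 to 16.7 percentage points over this range.

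**Step 5: what a split by Week 6 status could show.** At the reference rate of 2.5%, the expected number below the LLN is 30 × 0.025 = 0.75, and the chance of at least one is 1 − 0.975^30 = 53%. If k infants are low and all k are seroprotected, the lower 95% limit is 0.025^(1/k): 2.5%, 15.8%, 29.2%, 39.8% and 47.8% for k = 1 to 5. If none is, the upper limits are 97.5%, 84.2%, 70.8%, 60.2% and 52.2%. Such a display describes individual infants and cannot estimate a rate.

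**The case against.** The strongest reply is that the information exists. Vaccines given are recorded per infant, all B-cell data are listed (SAP 4.6.6), and all immune responses are listed (SAP 4.5.3). This stands. A reader might infer that the trial cannot tell a depleted infant who failed to respond from one who was never vaccinated. The documents do not support that, because the facts needed are held for each infant. The gap lies in the planned summaries. It is not fully closed by the listings, since the SAP names no listing of infant vaccinations: its vaccination-history outputs in 4.3.1 are for women, and the infant medication tables in 4.8.7 are not by B-cell status.

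A reader might also infer that MMR will be withheld or delayed in infants with low counts. Protocol 4.5.4 contains no such rule. It keeps the national schedule as default and says only that the result may be informative. Repeat counts are optional, and a later value could supersede the Week 6 one. Nor does deferral mean non-receipt: the final sample is timed from the MMR dose, so a deferred dose moves the sample with it. The Month 13 branch applies only where MMR is not planned.

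The B-cell sentence singles out live vaccines, so any link between B-cell status and receipt concerns MMR. For the other vaccines the only gap is the missing display by B-cell status. Finally, the stated objective concerns potentially exposed infants, which the exposure-timing subgroup addresses. That is fair, but it does not cure the pooling of MMR recipients with non-recipients within each exposure group.

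**Conclusion.** The point holds as a defect of the planned outputs. The pooling rule in SAP 4.5.3, with an analysis set that does not require vaccination, makes the MMR seroprotection figure count an unvaccinated infant exactly as a vaccinated non-responder. Protocol 4.5.4 gives a reason why non-receipt may be related to Week 6 B-cell status, and no titre or seroprotection summary is shown by that status.

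For 1 to 5 unvaccinated infants of 30, pooled seroprotection is understated by 3.3 to 16.7 points if all recipients respond and no unvaccinated infant is seroprotected. The shift vanishes if every infant receives MMR before sampling. The documents give no expected uptake, so the size is illustrative. Mean MMR titres are pooled in the same way, but the documents give no titre distribution from which to size that effect. No sample size or error rate depends on this point. It is a cheap improvement to the SAP and casts no doubt on the primary endpoint.

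**What to change.** In SAP 4.5.3 and 4.5.3.1, replace the MMR pooling rule. Report MMR titres and seroprotection among infants who received MMR, by number of doses at sampling (the final visit may follow a first or a second dose), and show infants without MMR separately.

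Add one descriptive display pairing each infant's Week 6 CD19+ count and LLN status (below, at or above, not measured) with vaccine doses, dates and each titre. Use a cross-table, or a listing if few infants are low.

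Do not code vaccines as on schedule or deferred against national schedules: the protocol records vaccines given, not deferrals or reasons. State in the SAP that no inferential claim will be made from the infants below the LLN.

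The cost is one table or listing with very small cells. No new data are needed. The SAP's tetanus and diphtheria sensitivity analysis already relies on infant dose number and timing.

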4.6 TREATMENT, PATIENT, STUDY, AND SITE DISCONTINUATION

4.6.1 Study Treatment Discontinuation

The decision to discontinue a woman from treatment lies with the treating physician, in agreement with the woman's wishes, and is not regulated by this protocol.

The primary reason for study treatment discontinuation should be documented on the appropriate eCRF page. In case the woman switches to another treatment for MS, the DMT should also be documented on the appropriate eCRF page.

4.6.2 Discontinuation from the Study

Women and their unborns/infants have the right to voluntarily withdraw from the study at any time for any reason. In addition, the investigator has the right to withdraw a woman from the study at any time. Women who decide to discontinue the study (this includes discontinuation of either the mother or the infant) are invited to attend an early study discontinuation visit (which may be conducted virtually or by telephone) as soon as possible (further details in Section 3.1.5).

Reasons for woman discontinuation from the study may include, but are not limited to, the following:

- Woman withdrawal of consent.
- Study termination or site closure.
- Adverse event.
- Loss to follow-up.
- Any medical condition that the investigator or Sponsor determines may jeopardize the safety of the woman, unborn or infant if he or she continues in the study.
- Woman's non-compliance, defined as failure to comply with protocol requirements as determined by the investigator or Sponsor.

Every effort should be made to obtain a reason for woman discontinuation from the study. The primary reason for discontinuation from the study should be documented on the appropriate eCRF (see Section 3.1.5). Women who withdraw from the study will not be replaced.

4.6.3 Study Discontinuation

The Sponsor has the right to terminate this study at any time. Reasons for terminating the study may include, but are not limited to, the following:

- The incidence or severity of adverse events in this or other studies indicates a potential health hazard to women in the study.
- Enrollment is unsatisfactory.

The Sponsor will notify the investigator if the Sponsor decides to discontinue the study.

4.6.4 Site Discontinuation

The Sponsor has the right to close a site at any time. Reasons for closing a site may include, but are not limited to, the following:

- Excessively slow recruitment.
- Poor protocol adherence.
- Inaccurate or incomplete data recording.
- Non-compliance with the International Council on Harmonisation of Technical Requirements for Registration of Pharmaceuticals for Human Use (ICH) guideline for GCP.
- No study activity (i.e., all women and their infants have completed the study and all obligations have been fulfilled).

5. ASSESSMENT OF SAFETY

SAFETY REPORTING REQUIREMENTS FOR STUDIED 5.1 **MEDICINAL PRODUCTS**

5.1.1 Safety Parameters and Definitions

The reporting requirements in this section apply to ocrelizumab and any other treatments used as co-administered products (i.e., premedication), according to the label. For a list of products, see Section 4.3.

For safety reporting requirements for non-studied medicinal products, see Section 5.2.

Safety assessments will consist of monitoring and recording serious adverse events and non-serious adverse events (including adverse events of special interest), performing safety laboratory assessments, measuring vital signs, and conducting other tests that are deemed critical to the safety evaluation of the study as per standard medical practice.

5.1.1.1 Adverse Events

According to the ICH, an adverse event is any untoward medical occurrence in a patient or clinical investigation patient administered a pharmaceutical product, regardless of causal attribution. An adverse event can therefore be any of the following:

- Any unfavorable and unintended sign (including an abnormal laboratory finding), • symptom, or disease temporally associated with the use of a medicinal product, whether or not considered related to the medicinal product.
- Any new disease or exacerbation of an existing disease (a worsening in the • character, frequency, or severity of a known condition), except as described in Appendix 5.
- Recurrence of an intermittent medical condition (e.g., headache) not present at • baseline.
- Any deterioration in a laboratory value or other clinical test (e.g., ECG, X-ray) that is • associated with symptoms or leads to a change in study treatment or concomitant treatment or discontinuation from study medicine.

Adverse events and serious adverse events related to MS are not considered for recording in the eCRF, unless they meet specific criteria. For more details, refer to Section 5.1.1.2.

5.1.1.2 Assessment of Serious Adverse Events and Non-Serious Adverse Events of Special Interest (Immediately Reportable to the Sponsor) and Other Non-Serious Adverse Events

Serious Adverse Events

A serious adverse event is any adverse event that meets any of the following criteria:

Is fatal (i.e., the adverse event actually causes or leads to death).

Ocrelizumab—F. Hoffmann-La Roche Ltd

- Is life-threatening. (NOTE: The term "life-threatening" refers to an event in which the patient was at immediate risk of death at the time of the event; it does not refer to an event that hypothetically might have caused death if it were more severe.)
- Requires or prolongs inpatient hospitalization.
- Results in persistent or significant disability/incapacity (i.e., the adverse event results in substantial disruption of the patient's ability to conduct normal life functions).
- Is a congenital anomaly/birth defect in a neonate/infant born to a mother exposed to study medicine.
- Is a significant medical event in the physician's judgment (e.g., may jeopardize the patient or may require medical/surgical intervention to prevent one of the outcomes listed above).

The terms "severe" and "serious" are not synonymous. Severity refers to the intensity of an adverse event (e.g., rated as mild, moderate, or severe, or according to the National Cancer Institute Common Terminology Criteria for Adverse Events (NCI CTCAE) criteria; see Appendix 5); the event itself may be of relatively minor medical significance (such as severe headache without any further findings).

Severity and seriousness need to be independently assessed for each adverse event recorded on the eCRF (for detailed instructions, see Appendix 5).

Non-Serious Adverse Events of Special Interest

Adverse Events of Special Interest (AESI) for this study include the following:

- Cases of potential medicine-induced liver injury that include an elevated ALT or AST in combination with either an elevated bilirubin or clinical jaundice, as defined by Hy's law (see Appendix 5).
- Suspected transmission of an infectious agent by the study medicine, as defined below:

Any organism, virus, or infectious particle (e.g., prion protein transmitting transmissible spongiform encephalopathy), pathogenic or non-pathogenic, is considered an infectious agent. A transmission of an infectious agent may be suspected from clinical symptoms or laboratory findings that indicate an infection in a patient exposed to a medicinal product. This term only applies when a contamination of the study medicine is suspected.

A. Non-Serious Adverse Events other than Adverse Events of Special Interest

All non-serious adverse events (in addition to adverse events of special interest) must be collected for this study, and coded according to the appropriate level of Medical Dictionary for Regulatory Activities (MedDRA) classification.

B. Specific Adverse Events that are exempt from collection

Adverse events and serious adverse events related to MS are not considered for recording in the eCRF. Medical occurrences or symptoms of deterioration that are anticipated as part of MS or which are expected in the patient population studied should be recorded as an adverse event only if judged by the physician to have unexpectedly worsened in severity or frequency or changed in nature at any time during the study.

Following the above rationale, the following events will not be considered as adverse events for this study:

- 1. MS relapses.
- 2. Disability progression (increase in EDSS or other scales performed by the physician).
- 3. MRI activity (new/enlarged T2 or T1 gadolinium-enhancing lesion in spinal or brain MRI), **unless** the activity is suggestive of a serious adverse event such as PML. In this case, information should be recorded in the section "PML" of the eCRF.
- 4. MS signs and symptoms.

Although these adverse events are not being actively solicited, the investigator/patients are reminded of the possibility to report any adverse reactions (for which they suspect a causal role of a medicinal product) that come to their attention to the Sponsor of the suspected medicinal product, or to the concerned competent authorities via the national spontaneous reporting system.

5.1.2 Methods and Timing for Capturing/Assessing Safety Parameters

The investigator is accountable for ensuring that all adverse events collected as per protocol (see Section 5.1.1 for definition) are recorded in the Adverse Event eCRF and reported to the Sponsor in accordance with instructions provided in this section and in Section 5.1.3.

For each adverse event recorded in the adverse event section of the eCRF, the investigator will make an assessment of seriousness (see Section 5.1.1.2), severity (see Appendix 5), and causality (see Appendix 5).

